Objective 2 is a pragmatic cluster randomized trial. We have partnered with two rural healthcare systems (one in eastern Kentucky and one in Western Kentucky) for this study. Two clinics from each system will be randomized to participate in the intervention (4 total intervention sites) and the remaining clinics will serve as the control sites. The intervention consists of health information technology (including an automated patient identification system and bidirectional e-referral system connecting clinics to the DSMES providers) and a practice facilitation collaborative. The collaborative is a structured, facilitated process that brings together teams from different organizations to learn from one another. The collaborative utilizes the Model for Improvement, a quality improvement approach designed by the Institute for Healthcare Improvement that uses rapid cycle quality improvement – repeated PDSA (plan do study act) cycles meant to identify care quality barriers and rapidly implement and measure change. Teams from intervention clinics will apply this quality improvement strategy to identify and address quality gaps in diabetes care and DSMES utilization at their clinics. Practice facilitators on the study team will provide individualized coaching (practice facilitation) to clinics in the intervention arm of the study. We will assess the effect of the interventions on DSMES referrals (primary outcome), by comparing rates of referrals between intervention and control clinics (clinics within the healthcare system not randomized to the intervention). Secondary outcomes include DSMES attendance, patient satisfaction and diabetes knowledge, A1c control, and intervention feasibility and acceptability.

Objective 3 involves surveys and interviews with clinic staff that participated in the intervention and DSMES providers from the geographic areas where the intervention took place. Interviews will be conducted via phone and audio will be recorded. The goal of Objective 3 is to understand how the various implementation strategies embedded within the practice facilitation collaborative and clinical context influenced DSMES uptake to inform future refinement for program replication and scale-up.

Attachments

Subject Recruitment Methods & Advertising

Describe how the study team will identify and recruit subjects. Please consider the following items and provide additional information as needed so that the IRB can follow each step of the recruitment process.

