Objective 2: Baseline measures include patient demographics (sex, race/ethnicity, insurance coverage, rural/urban distribution), A1c control (mean A1c, % of patients with A1c >9%) and blood pressure. Clinics will also report number of DSMES referrals and DSMES attendance from the 9-month baseline period. In addition to baseline data, control and intervention clinics will generate monthly reports from their electronic health record system to track DSMES referrals and A1c control. DSMES attendance will also be reported by the clinics based on feedback data from the bidirectional referral system linking clinics with DSMES providers. All data will be examined at the clinic level and will be de-identified/aggregated to the clinic level prior to being shared with our study team. The following data is being extracted from patient electronic health records by clinic staff: DSMES referrals (% referred/% eligible at the clinic level), DSMES attendance (% attended/% referred at the clinic level), A1c Data (mean A1c levels and % with A1c >9% at the following time points will be extracted from electronic health record data and de-identified/aggregated into intervention vs control clinics as well as for the subset of patients within intervention vs control clinics that attended DSMES: baseline, monthly during the intervention and for the 6 months following intervention. In addition to the data being extracted from patients' electronic health records, we will also be receiving data from the DSMES providers on patient satisfaction with the class and diabetes knowledge. This outcome will be reported to the study team monthly for all patients from study clinics who attended DSMES classes during the 9-month study + 6 month follow-up period. Patient satisfaction and diabetes knowledge will be evaluated using de-identified data from patient surveys that are routinely collected by DSMES providers for all individuals immediately following DSMES attendance. KDPH will provide the study team with de-identified data for all patients from the two participating healthcare systems who attend DSMES (aggregated to the clinic level). All data used in Objective 2 is data that is routinely collected; no additional data will be collected as a part of the study.

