For the primary study population (clinic staff and DSMES providers), informed consent will be obtained virtually from each primary participant at entry into the study by a trained study team member. Clinic staff and DSMES providers may participate in the learning collaborative either virtually or in-person. We are requesting a waiver of informed consent for our primary and secondary study population (patients).

V. Data Quality and Management

A. Data completeness and accuracy: The study team will work with intervention clinics to validate reporting of study data from their electronic health record systems. The validation process will occur during study months 6 to 9. Thereafter, intervention clinics will report data monthly to the study team who will assess the data for completeness and accuracy.

B. Data integrity and protection of databases: Study data obtained from secure clinic electronic health record systems and through surveys/interviews with providers and staff will be stored in a password protected, cloud-based database only accessible to study team members.

VI. Confidentiality

Primary participants in the intervention will be informed that participation is not anonymous due to the collaborative nature of the intervention; however, any data collected from the primary participants, e.g., demographic descriptors or qualitative feedback about the QI process, will be de-identified and/or disseminated in aggregate with other primary participant data. Secondary participants are patients. The study team will not have access to any patient-level identifiable information. The study team will be relying on routinely collected data that is de-identified and aggregated by clinic staff to evaluate outcomes. No identifying information will be used in any report or publication that is produced as part of this study; data will be presented only in the aggregate.

[Back to Top](#)

Future Use and Sharing of Material (e.g., Data/Specimens/Information)

If the material collected for this study will be used by members of the research team or shared with other researchers for future studies, please address the following:

- list the biological specimens and/or information that will be kept
- briefly describe the types, categories and/or purposes of the future research
- describe any risks of the additional use
- describe privacy/confidentiality protections that will be put into place
- describe the period of time specimens/information may be used

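### Referrals, the primary outcome, are counted from clinic EHR reports while the intervention includes an e-referral system, so a change in recording alone could separate the arms, and no two-arm counting rule or check would show it.

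*Combined protocol and SAP*

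**What the plan says.** Study Design, Objective 2, names the outcome: "We will assess the effect of the interventions on DSMES referrals (primary outcome"), comparing referral rates between intervention and control clinics. It describes the technology part of the intervention as "including an automated patient identification system and bidirectional e-referral system connecting clinics to the DSMES providers".

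Research Procedures, Objective 2, gives the data source: "control and intervention clinics will generate monthly reports from their electronic health record system to track DSMES referrals and A1c control". The measure is "DSMES referrals (% referred/% eligible at the clinic level"), extracted and aggregated by clinic staff. For the earlier period, "Clinics will also report number of DSMES referrals and DSMES attendance from the 9-month baseline period".

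The Data and Safety Monitoring Plan, section V.A, describes quality control: "The study team will work with intervention clinics to validate reporting of study data from their electronic health record systems", during study months 6 to 9. It continues: "Thereafter, intervention clinics will report data monthly to the study team who will assess the data for completeness and accuracy". Control clinics are not mentioned in either sentence.

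The visible text does not say what event counts as a referral, how fax, paper, phone or verbal referrals are counted, or whether one rule covers both arms and both periods. Data Collection & Research Materials points to an attached Data Collection Summary, which is not shown.

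**The concern.** The intervention acts on the process that produces the outcome record. An e-referral system may increase the number of patients referred, which is the effect of interest. It may also change the share of referrals that a clinic's EHR report picks up, which is a measurement effect. An outcome counted only from that report cannot separate the two.

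Nothing described in the plan would reveal the difference. The study is unmasked and the study team sees only clinic-level aggregates. Report checking is described for one arm. The external data from the Kentucky Department of Public Health (KDPH) concern patients who attend DSMES, not referrals received.

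The sample size justification says that the pilot is to measure the approximate magnitude of effectiveness, and Objective 2 is to supply preliminary data for the planned R01. An effect estimate that contains a recording component could mis-size that trial.

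**Working it through.** The plan states no expected referral rate, capture rate, between-clinic SD or test, so there is no figure of its own to reproduce. The only referral rates in the documents are in Background: 0% rising to 31% in a quality improvement study of an electronic referral process with training. What follows is an illustration.

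**Inputs.** From the documents: 4 intervention and 7 control clinics (4 + 7 = 11), and a 9-month clinic-reported baseline. Assumed: a true referral rate p that is equal in both arms; capture c1 = 95% at intervention clinics and c0 at control clinics, where capture is the share of true referrals that appear in the report.

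**Step 1: formulas.** Observed rate = p × c. With no true effect, false difference = p × (c1 − c0) and false ratio = c1 / c0. The ratio does not depend on p.

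**Step 2: p = 15%.** Intervention clinics show 15% × 0.95 = 14.25%.
- c0 = 90%: control 13.5%, difference 0.75 points, ratio 0.95/0.90 = 1.06.
- c0 = 70%: control 10.5%, difference 3.75 points, ratio 0.95/0.70 = 1.36.
- c0 = 50%: control 7.5%, difference 6.75 points, ratio 0.95/0.50 = 1.90.
- c0 = 95%: difference 0, ratio 1.00.

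**Step 3: range over the assumed true rate** (false difference in percentage points).

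| True rate | c0 = 90% | c0 = 70% | c0 = 50% |
|---|---|---|---|
| 5% | 0.25 | 1.25 | 2.25 |
| 10% | 0.5 | 2.5 | 4.5 |
| 15% | 0.75 | 3.75 | 6.75 |
| 20% | 1.0 | 5.0 | 9.0 |
| 31% | 1.55 | 7.75 | 13.95 |

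**Step 4: reverse direction.** Suppose e-referrals sit partly outside the EHR report, so that capture is 70% at intervention clinics and 95% at control clinics. At p = 15% the difference is 15% × (0.70 − 0.95) = −3.75 points and the ratio is 0.70/0.95 = 0.74. A real benefit would then be hidden.

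**Step 5: does the baseline help?** Suppose both arms had capture of 70% at baseline and only the intervention arm rises to 95%. At p = 15% the difference in differences is (14.25 − 10.5) − (10.5 − 10.5) = 3.75 points, so the artefact stays in full. If capture differs between arms but is stable, 95% against 70% in both periods, it is (14.25 − 14.25) − (10.5 − 10.5) = 0. Baseline adjustment removes a standing difference in recording, but not a change brought about by the intervention.

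**Step 6: would noise swamp it?** Take p = 20%, an assumed between-clinic SD of 4 points, and a two-sided 5% t test on 4 against 7 clinic rates (9 degrees of freedom). The standard error is 4 × √(1/4 + 1/7) = 2.51 points. Artefacts of 1.0, 5.0 and 9.0 points give noncentrality of about 0.40, 1.99 and 3.59, and a chance of a false-positive result of about 7%, 43% and 89%. A small recording gap would be lost in the noise; a large one would not.

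**The case against.** A reader might infer that the e-referral system replaces the existing channel and makes every referral a countable record, so that a positive result would be an artefact. The documents do not support that. Study Design says only that the system is part of the intervention. No section describes how control clinics refer or how an e-referral enters the EHR. Both arms report from the same type of source, and the controls are clinics in the same organisations chosen to be similar. If they already place referrals as EHR orders, the bias is small. Objectives speaks of secure messaging with a health information exchange as technology partner, so e-referrals might sit outside the clinic EHR and the bias might run the other way. Research Procedures also says that clinics report attendance from the bidirectional system without naming an arm. If control clinics had the system too, the gap would narrow, though that would sit badly with Study Design.

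All of this stands, and it limits what can be said about direction and size. So does the point that the Data Collection Summary may already define a referral.

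It can also be said that checking the reports in all 11 clinics would largely settle the matter. That holds in part. Such a check finds errors in the report, but it misses referrals never entered in the EHR unless the rule says that they count. Finally, this is a pilot. That lowers the stakes of a test result, but not of an effect estimate carried into a larger trial.

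**Conclusion.** The concern holds as a conditional risk. The primary count comes from EHR reports, the randomised package includes a system that may alter how referrals reach those reports, and report checking is described for one arm only. A recording difference could therefore be read as an intervention effect, and baseline adjustment would not remove a capture change confined to one arm.

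The likelier direction favours the intervention, since electronic referral and the described checks both sit in that arm. This is a judgement, not a finding from the text. With the assumed 95% capture at intervention clinics, the false ratio runs from 1.06 to 1.90 as control capture falls from 90% to 50%. It is 1.00 at equal capture and below 1 if e-referrals are missed. The true rate, the capture values, the SD and the t test are all assumptions. The change should be made, with medium confidence that the artefact would matter in practice.

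**What to change.** In Research Procedures, Objective 2, state one counting rule for all 11 clinics and for both baseline and follow-up: each referred patient counts once, whatever the channel, e-referrals included. In section V.A of the Data and Safety Monitoring Plan, extend the check of the report against that rule to control clinics. If the Data Collection Summary already holds such a rule, confirm that it covers all channels, both arms and both periods.

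If KDPH or the DSMES providers already log referrals received by clinic, obtain that aggregate count and repeat the primary comparison with it as a sensitivity analysis.

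The rule costs a few sentences. The check adds work at seven control clinics. The provider count is a new data request, because KDPH is described as supplying data on attendees. It fits the plan's commitment to use only routinely collected data only if the log already exists. It would omit other DSMES programmes, and the e-referral system may improve logging at the provider end as well. It therefore supports the EHR count and does not replace it.

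The change log shows enrolment marked closed in December 2024, with an anticipated end date of 4/1/2026, so some reports may already exist. Where they do, apply the rule to stored records as far as they allow. If no provider log exists, report the effect with the possible recording artefact stated as a limitation wherever it is used to plan the R01.

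### Outcome measurement may depend on arm: data checks are described for intervention clinics only, and attendance is reported from feedback in the intervention's own e-referral system

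*Combined protocol and SAP*

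**What the plan says.** **Who supplies data.** Research Procedures, Objective 2, states that "control and intervention clinics will generate monthly reports from their electronic health record system to track DSMES referrals and A1c control". Study Design makes the primary analysis a comparison of referral rates between intervention and control clinics, so reports from both arms feed it. For the period before the intervention, "Clinics will also report number of DSMES referrals and DSMES attendance from the 9-month baseline period".

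**Who is checked.** The Data and Safety Monitoring Plan (DSMP), section V.A, says "The study team will work with intervention clinics to validate reporting of study data from their electronic health record systems" and "The validation process will occur during study months 6 to 9". It continues: "Thereafter, intervention clinics will report data monthly to the study team who will assess the data for completeness and accuracy". The text available gives no matching step for control clinics. It also does not say whether validation reaches back to the baseline reports.

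**Where attendance comes from.** Research Procedures says "DSMES attendance will also be reported by the clinics based on feedback data from the bidirectional referral system linking clinics with DSMES providers". Study Design names the bidirectional e-referral system as one of the information-technology components of the intervention. The same Research Procedures paragraph also puts attendance among the items that clinic staff extract from the EHR: "DSMES referrals (% referred/% eligible at the clinic level), DSMES attendance (% attended/% referred at the clinic level". It asks for A1c by arm "as well as for the subset of patients within intervention vs control clinics that attended DSMES: baseline, monthly during the intervention". An EHR record of attendance is therefore presumed in control clinics and at baseline, but how attendance gets into that record is not described.

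**A further source.** KDPH is to supply clinic-level, de-identified data on DSMES attendees from both healthcare systems. The text describes these data for patient satisfaction and diabetes knowledge, not for the attendance outcome.

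**The concern.** Randomisation balances the clinics. It does not protect against measuring them differently afterwards. If reports are corrected in one arm and left alone in the other, or if one arm gains a feedback channel that the other lacks, a difference in capture can look like a treatment effect or hide one.

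The exposure is greater here than in many trials. Clinic staff extract and aggregate the data, the study team sees no identifiable patient-level records, and the study is unmasked. Section V.A contains the only check on outcome data in the available text. Both outcomes are ratios, so numerator and denominator can each be affected. DSMP III.A says the pilot is to estimate the approximate magnitude of effectiveness, and Objective 2 is to give preliminary data for a planned R01. A distorted estimate would carry forward into that study.

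**Working it through.** The plan gives no capture rate, power figure or effect size, so there is no figure of its own to reproduce. The check is a comparison of passages, followed by an illustration.

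**Step 1. Text side by side.**

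| Item | Intervention clinics (4) | Control clinics (7) |
|---|---|---|
| Monthly EHR reports of referrals and A1c | Yes | Yes |
| Report validation, study months 6 to 9 | Yes | Not stated |
| Monthly completeness and accuracy check | Yes | Not stated |
| Attendance feedback through e-referral | Yes, an intervention component | Not stated how obtained |
| Attendance listed as EHR-extracted | Yes | Yes, route into the EHR not stated |

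The clinic counts agree: 4 + 7 = 11, and 2 clinics in each of 2 systems = 4. Clinics with no stated check: 7/11 = 64%.

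**Step 2. What unequal capture would do (illustration only; every capture rate is assumed).** Let q = numerator capture / denominator capture. With no true effect, the follow-up comparison shows a spurious ratio of q_I / q_C. Set q_I = 1 (equal numerator and denominator capture in intervention clinics). The spurious difference is then p × (1 − q_C), where p is the true proportion in both arms. Three values of p are assumed: 10% and 31% for referrals, 40% for attendance. The 31% is the post-change referral rate of a quality improvement study cited in Background, used only for scale.

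| Control capture, numerator/denominator | q_C | Ratio | Points at p = 10% | at 31% | at 40% |
|---|---|---|---|---|---|
| 90/95% | 0.947 | 1.06 | +0.5 | +1.6 | +2.1 |
| 95/90% | 1.056 | 0.95 | −0.6 | −1.7 | −2.2 |
| 60/60% | 1.000 | 1.00 | 0 | 0 | 0 |
| 60/80% | 0.750 | 1.33 | +2.5 | +7.8 | +10.0 |
| 80/60% | 1.333 | 0.75 | −3.3 | −10.3 | −13.3 |

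**Step 3. Would a baseline comparison remove it?** The spurious ratio of changes is (q_I,post / q_I,base) / (q_C,post / q_C,base).

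- Capture constant over time in each arm: 1.00, whatever its level.
- Validation moves intervention clinics from q = 0.75 to 1 and controls do not change: 1 / 0.75 = 1.33.
- Validation moves intervention clinics from q = 1.333 to 1 and controls do not change: 1 / 1.333 = 0.75.
- Baseline rerun under the validated specification, so that q_I,base = q_I,post, and controls constant: 1.00.

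Adjustment for baseline therefore removes only differences that stay constant. The second and third cases assume that baseline reports were not validated, which the documents leave open. With the same capture in both arms, the spurious ratio is 1.00 at any true rate.

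**The case against.** **The wording may be loose.** Study Population describes all 11 clinics as taking part in the intervention, in both Objective 2 and Objective 3. Section V.A also mentions monthly reporting for intervention clinics alone, although Research Procedures has both arms reporting. So V.A may be an incomplete account of the data flow. This stands as a reason for caution. Against it, Study Design and DSMP III.A, the latter in the same plan as V.A, clearly separate four intervention clinics from seven controls. The one-arm reading remains the more natural one.

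**The clinics share organisations.** Randomisation is within each healthcare organisation. If reports are built at organisation level, validating them for one arm would serve both. The documents do not say whether this is so.

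**An attachment may settle the attendance source.** Data Collection & Research Materials refers to a Data Collection Summary for the complete list, and it is not in the text available. The two descriptions of attendance may also be compatible, for example if e-referral feedback is filed in the EHR. This stands. What remains unanswered in the text is how a control clinic, or any clinic at baseline, learns that a patient attended.

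**The scenarios are not evidence.** This is correct. They run from 0.75 to 1.33 through 1.00 and rest on assumed inputs. A reader might infer that the asymmetry favours the intervention, since missed events in control clinics would inflate the effect. The documents do not support that: over-counted numerators or missed denominators in unvalidated control reports would act the other way.

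**Conclusion.** The point holds as a risk. Followed as written, the plan checks outcome reports in one arm and reports attendance from feedback in a system that belongs to the intervention. The first matter touches the primary outcome (referrals) and A1c; the second touches attendance, a secondary outcome. The size and direction of any bias are unknown for both.

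The conclusion rests on reading V.A literally and on the absence of the Data Collection Summary from the text. A reader might go further and infer that control data are in fact unchecked, or that control clinics have no attendance data at all. The documents support neither: the first is silence in one section, and attendance is also listed as EHR-extracted for both arms. Nor does it follow that the KDPH attendee data should replace the planned source. As described, they are clinic-level aggregates that cannot be linked to referrals. Attendees who were never referred could enter the numerator, and the outcome would no longer be attended among referred.

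This should be fixed; confidence is moderate.

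**What to change.** 1. **DSMP V.A.** Replace *intervention clinics* with *all 11 clinics (intervention and control)*. Apply one report specification, defining numerator and denominator, and the same validation, completeness and accuracy checks to the baseline, intervention and follow-up reports. The Protocol Changes log shows the field for open enrolment or new data collection switched to No in December 2024. If collection has ended, rerun the common specification where records allow, report validation status by arm, and state as a limitation whatever cannot be rerun.

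2. **Research Procedures, Objective 2.** Define attendance from one EHR-recorded source used the same way in both arms and all periods. State how attendance reaches that record in control clinics and at baseline. Treat e-referral feedback as an intervention-arm process measure. If the Data Collection Summary already names the source, bring that statement into the protocol text.

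3. **Cross-check.** Use the KDPH clinic-level attendee counts only as an arm-neutral check, for example attendees per eligible patient by clinic. Note that they cannot be linked to referrals as described, may not cover baseline, and may miss programs outside KDPH (Background counts 90 accredited programs in the state).

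4. **Reporting.** Label any capture-rate scenario as illustration only.

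The cost is modest extra study-team and clinic time for seven clinics in the same two systems, since one specification can be reused. A retrospective rerun depends on access to records. The anticipated project end date is 4/1/2026.

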In this study, we propose implementing health information technology, including automated patient identification and bidirectional secure messaging between clinicians and DSMES providers, and using practice facilitation to address referral barriers and increase clinician awareness and motivation. We have partnered with KDPH (statewide DSMES provider), Kentucky Regional Extension Cooperative (KY-REC, practice facilitation partner), Kentucky Health Information Exchange (health information technology (HIT) partner) and two healthcare systems in rural Kentucky. Our proposal builds on a diabetes quality improvement collaborative facilitated by KY-REC and KDPH that demonstrated increased DSMES utilization. We will use a rigorous study design to evaluate implementation processes and effectiveness by testing the hypothesis that patient identification and referral strategies, bidirectional linkages between clinics and DSMES providers, and primary care clinician engagement will increase DSMES utilization through the following objectives:

Objective 1 – Planning: To use an established implementation science framework (PRISM) to identify determinants of DSMES uptake in Kentucky by interviewing previous DSMES quality improvement collaborative stakeholders, and to adapt the previous intervention using implementation mapping to connect stakeholder determinants to intervention strategies and outcomes.

Objective 2 – Implementation: To implement an intervention comprised of health information technology and a practice facilitation collaborative with two healthcare systems in rural Kentucky to increase DSMES referral rates and gather preliminary data for the planned R01 study.

Objective 3 – Evaluation: To evaluate the pragmatic implementability of the intervention by assessing the feasibility, acceptability, and sustainability of the intervention via stakeholder and participant survey, administrative and interview data.

Study Design

Describe and explain the study design (e.g., observational, secondary analysis, single/double blind, parallel, crossover, deception, etc.).

- **Clinical Research:** Indicate whether subjects will be randomized and whether subjects will receive any placebo.
- **Community-Based Participatory Research:** If you are conducting [community-based participatory research \(CBPR\)](#), describe strategies for involvement of community members in the design and implementation of the study, and dissemination of results from the study.

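### Clinic-reported DSMES attendance, a secondary outcome, rests on feedback from a referral system that is part of the randomised intervention, and the control clinics' source is not described

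*Combined protocol and SAP*

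**What the plan says.** DSMES attendance is listed as a secondary outcome of the cluster randomised pilot (Study Design, Objective 2); referrals are primary. Three statements bear on where attendance data come from.

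- **Source.** Research Procedures, Objective 2: "DSMES attendance will also be reported by the clinics based on feedback data from the bidirectional referral system linking clinics with DSMES providers".
- **Intervention.** Study Design, Objective 2: "The intervention consists of health information technology (including an automated patient identification system and bidirectional e-referral system connecting clinics to the DSMES providers". The Objectives section puts the same linkage into the tested hypothesis, namely that "bidirectional linkages between clinics and DSMES providers, and primary care clinician engagement will increase DSMES utilization". Controls are defined only by allocation, in the phrase "comparing rates of referrals between intervention and control clinics (clinics within the healthcare system not randomized to the intervention".
- **Checks.** Data and Safety Monitoring Plan, section V, describes validation of EHR reporting in study months 6 to 9, then monthly review for completeness and accuracy. Both are written for intervention clinics.

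The same Research Procedures paragraph also points to a common source. It says "The following data is being extracted from patient electronic health records by clinic staff" and includes in that list "DSMES attendance (% attended/% referred at the clinic level", with no limit by arm. It asks clinics for attendance over a 9-month baseline, and plans A1c summaries for attendees within intervention and control clinics. The sentence that names both arms is narrower: "control and intervention clinics will generate monthly reports from their electronic health record system to track DSMES referrals and A1c control". Attendance is not in it.

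**The concern.** An outcome should be recorded in the same way in both arms. Here the channel that tells a clinic that a referred patient attended is, on the Study Design text, something the intervention supplies. A control clinic without it would have to learn of attendance at an outside provider by another route. If that route is less complete, or more complete, the arms differ in recorded attendance even when true attendance is equal.

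The pilot is meant to give a rough size of effect (Data and Safety Monitoring Plan, section III) and to "gather preliminary data for the planned R01 study". A capture artefact in attendance could carry into that planning, and attendance measures utilisation more directly than referral does. Two further uses are exposed:

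- Change from baseline, if the system was not yet running in the baseline period.
- The A1c comparison among attendees, if who counts as an attendee depends on arm.

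With checks described for intervention clinics only, no step in the visible text would reveal such a gap.

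**Working it through.** The plan states no attendance rate, capture rate, power or effect size, so it has no figure to reproduce. The only inputs taken from the documents are the clinic counts: 4 intervention + 7 control = 11.

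**Step 1: the three possible readings.**

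- The attendance sentence covers both arms and controls lack the system. Controls are then asked to report from a source they do not have.
- The sentence covers intervention clinics only. The control source is then unstated.
- All 11 clinics have the system. The capture concern then largely falls away, but the Study Design description of what is randomised needs reconciling with it.

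Each reading calls for a statement of source by arm.

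**Step 2: what unequal capture would do (all inputs assumed).** With no true effect,

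spurious difference = true attendance × (intervention capture − control capture).

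| Capture, intervention vs control | True attendance 50% | True attendance 30% |
|---|---|---|
| 95% vs 95% | 47.5 − 47.5 = 0 points | 28.5 − 28.5 = 0 points |
| 95% vs 85% | 47.5 − 42.5 = 5 | 28.5 − 25.5 = 3 |
| 95% vs 75% | 47.5 − 37.5 = 10 | 28.5 − 22.5 = 6 |
| 95% vs 60% | 47.5 − 30.0 = 17.5 | 28.5 − 18.0 = 10.5 |
| 75% vs 95% | 37.5 − 47.5 = −10 | 22.5 − 28.5 = −6 |

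**Step 3: size against the pilot's precision.** For an unstratified difference of clinic means with equal weights, SE = SD × √(1/4 + 1/7) = 0.627 × SD.

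- Assumed between-clinic SD of 10 points: SE 6.3, 95% half-width 2.262 × 6.27 = 14.2 points (t on 9 df). A 10-point artefact is 10/6.27 = 1.6 SE.
- Assumed SD of 15 points: SE 9.4, half-width 21.3 points. A 10-point artefact is 10/9.40 = 1.1 SE.

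**Step 4: would counting only KDPH attendance be safer?** Research Procedures has KDPH supply clinic-level data on attendees from both healthcare systems. That sentence sits with the satisfaction and knowledge surveys and is not assigned to the attendance outcome. KDPH is also not the only DSMES provider in the state (Background). If the e-referral link steers patients towards KDPH, the KDPH share of attendance differs by arm. At 50% true attendance, assumed shares of 90% against 90%, 75% or 60% give 45% against 45%, 37.5% or 30%, which is 0, 7.5 or 15 spurious points. KDPH-only counting is better only if the arm gap in KDPH share is smaller than the arm gap in capture. Neither gap is known.

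**The case against.** The strongest reply is that the premise is inferred. No passage says that control clinics lack the system. The attendance sentence speaks of clinics generally and follows directly on a sentence naming both arms. The Study Population text for Objective 2 describes all 11 clinics as taking part in the intervention, and the Objectives section speaks of implementing it with two healthcare systems. Those lines conflict with the four intervention sites in Study Design, so they do not show that controls have the system, but they make the inference less secure.

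The plan also assumes a control-clinic route. Baseline attendance, the EHR listing and the A1c subset in both arms all require that attendees can be identified without the intervention. This stands: a route is presupposed, though not described. The Data Collection Summary may describe it.

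Three further points also stand. Attendance is one of several secondary outcomes in a pilot, and the primary outcome has a stated EHR source in both arms. The illustrative artefact of 10 points is smaller than the illustrative half-widths of 14.2 and 21.3 points, which limits how far the estimate could mislead, though imprecision does not excuse bias. And KDPH-only counting is not shown to be less biased.

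What does not follow is that nothing needs changing. Taken as written, the attendance sentence ties the measurement to an intervention component, and the described checks leave out the comparison arm.

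**Conclusion.** The concern holds in conditional form. The stated source of clinic-reported attendance is a component of the randomised intervention, the control-clinic route is assumed but not described, and data checks are described for intervention clinics only. If control clinics lack the system, capture could differ by arm.

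The documents do not allow the size or direction to be estimated. The figures above, from −10 to +17.5 points, are illustrations in which everything except the 4 and 7 clinics is assumed.

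A reader might infer that control clinics do lack the system, so that the attendance result is biased in favour of the intervention. The documents do not support that: absence of the system is never stated, and worse capture in the intervention arm would reverse the sign. A reader might also infer that the referral outcome is affected by the same source problem. It is not, since referrals come from EHR reports in both arms; the intervention-only checks do cover referral data, but that is a separate matter.

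This should be fixed, with medium confidence. If all 11 clinics have the system, or the Data Collection Summary names a common source, a short statement of source by arm and period disposes of the capture question.

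**What to change.** 1. **One source for the between-arm comparison.** State the attendance source by arm and period, and use one obtained the same way in all 11 clinics. Report change from baseline only if that source also covers the baseline period. Do not use referral-system feedback for the comparison unless all 11 clinics have the system; otherwise report it as an intervention-arm process measure.
2. **KDPH data as a cross-check.** If KDPH confirms that its planned clinic-level data hold attendance counts, tabulate them by arm against clinic-reported attendance for the same months, as a cross-check or sensitivity analysis. Note that attendance at other providers is missed and may differ by arm. The KDPH data are described for the 9-month study and 6-month follow-up, not for baseline.
3. **Same checks in both arms.** Apply the section V completeness and accuracy checks to the seven control clinics, on the routine reports they already submit.
4. **A1c among attendees.** Treat this comparison as descriptive unless attendees are identified the same way in both arms.

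The cost is modest: one KDPH query, a source statement, and data checks at seven clinics. Validation was scheduled for study months 6 to 9, and the change log shows the item on openness to new subjects or data switched from Yes to No in December 2024. The checks may therefore have to be retrospective. If neither the common source nor the checks can be achieved, report the difference in source as a limitation.
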